Administration of vaccine ^j	X				
Serum sample for polio antibodies	X ^e			X	
Stool sample for viral culture/quantitative PCR, stool sample for potential poliovirus sequencing, stool sample for potential neurovirulence assay ^l	X-----X ^l		X	X ^l	X
Solicited systemic AEs (Diary) ^k	X-----X				
Remote contact for safety follow-up ^m					
Concomitant therapies ⁿ	X	X	X	X	X
Adverse events ⁿ	X	X	X	X	X
Reminder Code of Conduct ^o	X	X	X	X	X

- a. In case of early termination, the subjects will be asked to return to the clinical site within 14 days after discontinuation for assessments as outlined on Day 28.
- b. No study-related assessment is to be carried out before signing of the informed consent form.
- c. Including polio vaccination history.
- d. Includes weight and height at Day 0. After Day 0, symptom-directed physical examination.
- e. Prior to vaccination.
- f. Blood pressure and heart rate (supine) and oral body temperature. On Day 0, vital signs will be assessed prior to and 30 min after vaccination.
- g. For a list of assessments, please see Appendix 1: Overview of Laboratory assessments.

- h. In women of childbearing potential, a urine pregnancy test will be performed.
- i. Includes HBsAg, anti-HCV and anti-HIV antibodies, and IgA.
- j. The subjects will be kept under medical supervision for at least 30 min after vaccination.
- k. Solicited AEs will be collected for Days 0-7.
- l. Subjects will be asked to collect the first stool of every day in the provided container and to store this in the provided thermal bag with cooling elements: daily collection on Days 0 to 10 plus collection on Days 14, 21, V4 minus 1 or 2 days and V5 minus 1 or 2 days. At Day 0 the storage procedure will be explained and the collection material provided. Subjects who are still shedding virus in one of the 3 last stool samples will be asked to further collect 3 consecutive stool samples every 3 weeks till end of shedding.
- m. Remote contact (text message by sms, WhatsApp or email) on Day 3 and on Day 21 for safety follow-up and reminder stool collection scheme.
- n. Adverse events and intake of concomitant medication(s) will be monitored continuously from informed consent until the last study-related activity. The subjects can record unsolicited AEs on their diary card.

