- l. Subjects will be asked to collect the first stool of every day in the provided container and to store this in the provided thermal bag with cooling elements: after each vaccine dose, daily collection on Days 0 to 10 plus collection on Days 14, 21, V4 minus 1 or 2 days (= V7 minus 1 or 2 days after 2nd vaccination) and V8 minus 1 or 2 days. At Day 0, the storage procedure will be explained and the collection material provided. Subjects who are still shedding virus in one of the 3 last stool samples will be asked to further collect 3 consecutive stool samples every 3 weeks till end of shedding.
- m. Remote contact (text message by sms, WhatsApp or email) on Day 3 and on Days 21, 31 and 49 for safety follow-up and reminder stool collection scheme.
- n. Adverse events and intake of concomitant medication(s) will be monitored continuously from informed consent until the last study-related activity. The subjects can record unsolicited AEs on their diary card.
- o. After signing on screening visit, weekly reminder Code of Conduct by email or sms and on each visit to emphasize the need and importance of hygienic measures and respecting the inclusion/exclusion criteria until end of study.

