9. STUDY TERMINATION/COMPLETION

9.1 STUDY COMPLETION

A subject will be considered to have completed the study if he or she has completed all study related procedures 42 days after the last study vaccination and shedding is PCR-negative on 3 consecutive stool samples (with a maximum of one sample per day).

However, if any AE or SAE, including clinically significant abnormalities in laboratory safety testing are observed subjects will continue to be followed until these are resolved or determined to be chronic or stable or until the event is otherwise explained.

Also, if type 2 virus shedding is detected by PCR on one of the last 3 scheduled stool samples the study duration for this individual will be extended. As soon as these results are known (anticipated approximately 3 weeks after the last such sample provided for evaluation) the subject will be asked to further collect 3 consecutive stool samples (with a maximum of one sample per day) after the last per-protocol sample, and to repeat this until shedding is PCR-negative for type 2 poliovirus on 3 consecutive stool samples.

If the last stool sample is missing, subject will be asked to provide a new sample as soon as possible in order to determine end of study for this person or the need for further stool sample collection according to the collection cadence until shedding is PCR negative on 3 consecutive stool samples.

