- b. No study-related assessment is to be carried out before signing of the informed consent form.
- c. Including polio vaccination history.
- d. Includes weight and height at Day 0. After Day 0, symptom-directed physical examination.
- e. Prior to vaccination.
- f. Blood pressure and heart rate (supine) and oral body temperature. On Day 0, vital signs will be assessed prior to and 30 min after vaccination.
- g. For a list of assessments, please see Appendix 1: Overview of Laboratory assessments.
- h. In women of childbearing potential, a urine pregnancy test will be performed.
- i. Includes HBsAg, anti-HCV, and HIV antibodies.
- j. The subjects will be kept under medical supervision for at least 30 min after vaccination.
- k. Solicited AEs will be collected for Days 0-7.
- l. Subjects will be asked to collect the first stool of every day in the provided recipient and bring the samples with them at the next scheduled visit. Daily collection on Days 0 to 10 plus collection on Days 14, 21 and V4 minus 1 or 2 days. Stool samples need to be stored by the subject at 4-8°C for maximum 7 days, before brought to the vaccine center. At Day 0 the storage procedure will be explained and the collection material provided.
- m. Daily remote contact (text message by sms, WhatsApp or email) from Day 0 to Day 10 and also on Day 21 and 42.

- n. Adverse events and intake of concomitant medication(s) will be monitored continuously from informed consent until the last study-related activity. The subjects can record unsolicited AEs on their diary card.

TIME AND EVENTS SCHEDULE – GROUP 2

Assessments	Group 2							Follow-up contact
	1	2	3	4	5	6	7	
Time of Visit (days)	D 0	D 7 (+/- 2D)	D 14 (+/- 3D)	D 28 (+/- 2D)	D 35 (+/- 2D)	D 42 (+/- 3D)	D 56 ^a (+/- 2D)	D 70 (+/- 4D)
Visit Window								
Informed consent ^b	X							
In-/exclusion criteria	X							
Medical history/concomitant diseases	X							
Medication history ^c	X							
Demographic data	X							
Physical examination ^d	X ^e	X		X ^e	X			X
Vital signs ^f	X ^{e,f}	X		X ^e	X			X
Clinical laboratory tests ^g	X ^e	X		X ^e	X			X
Pregnancy test ^h	X			X ^e				
Serology ⁱ	X							
Randomization	X							
Administration of vaccine ^j	X			X				
Serum sample for polio antibodies	X ^e			X ^e				X
Stool sample for viral culture/quantitative PCR ^l , stool sample for potential poliovirus sequencing, stool sample for potential neurovirulence assay	X----- X ^l	X	X----- X ^l		X			
Solicited systemic AEs (Diary) ^k	X----- X		X----- X					

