Remote contact for safety follow-up ^m	X-----X ^m		X-----X ^m					X
Concomitant therapies ⁿ	X	X	X	X	X	X	X	X
Adverse events ⁿ	X	X	X	X	X	X	X	X

- a. In case of early termination the subjects will be asked to return to the clinical site within 14 days after discontinuation for assessments as outlined on Day 56.
- b. No study-related assessment is to be carried out before signing of the informed consent form.
- c. Including polio vaccination history.
- d. Includes weight and height at Day 0. After Day 0, symptom-directed physical examination.
- e. Prior to vaccination.
- f. Blood pressure and heart rate (supine) and oral body temperature. On Day 0 and Day 28 (Group 2 only), vital signs will be assessed prior to and 30 min after vaccination.
- g. For a list of assessments, please see Appendix 1: Overview of Laboratory assessments.
- h. In women of childbearing potential, a urine pregnancy test will be performed.
- i. Includes HBsAg, anti-HCV, and HIV antibodies.
- j. The subjects will be kept under medical supervision for at least 30 min after vaccination.
- k. Solicited AEs will be collected for Days 0-7 and Days 28-35.

- p. Subjects will be asked to collect the first stool of every day in the provided recipient and bring the samples with them at the next scheduled visit. After each vaccine dose, daily collection on Days 0 to 10 plus collection on Days 14, 21 and V4 minus 1 or 2 days (=V7 minus 1 or 2 days after 2nd vaccination). Stool samples need to be stored by the subject at 4-8°C for maximum 7 days), before brought to the vaccine center. At Day 0 the storage procedure will be explained and the collection material provided.
- q. Daily remote contact (text message by sms, WhatsApp or email) from Day 0 to Day 10 and also on Day 21 after the first vaccine dose. Thereafter, daily remote contact from Day 28 to Day 38 and also on Day 49 and Day 70.
- r. Adverse events and intake of concomitant medication(s) will be monitored continuously from informed consent until the last study-related activity. The subjects can record unsolicited AEs on their diary card.

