6.7.1 Exploratory Viral Shedding Endpoints

Throughout, viral shedding analyses will be conducted by group and dose number. The descriptive summaries below will also be computed separately by site. Between-group inferential analyses will additionally be conducted among the site in common between UAM1 and UAM4, for OPV-vaccinated subjects, if the post-dose-1 between-site GMT comparison indicates a significant difference in immunogenicity between sites. The shedding analyses will be conducted considering all available samples, collected at Days 0-10, 14, 21, 28, and 42 following each dose (with day of vaccination defined as Day 0) and additional samples collected, as necessary, to define the end of shedding for participants. All viral shedding data will be listed, including both sample collection and assay results.

Categorical summaries of type 2 viral shedding positivity (positive via PCR) and continuous summaries of viral titers (\log_{10} CCID₅₀/g among both shedders and shedders/non-shedders combined) will be produced by group and by post-vaccination day. Each of these will be augmented with two-sided 95% confidence intervals. The Clopper-Pearson exact method will be used for shedding positivity rate, and the bootstrap method (10,000 replicates, quantile method) will be used for the median \log_{10} viral titers. Subjects who are PCR-negative for viral shedding at a given time point will be assigned the value of 0 for computations involving the \log_{10} CCID₅₀/g, and values PCR positive for type 2 poliovirus but below LLOQ ($2.75 \log_{10}$ CCID₅₀/g) or above ULOQ ($8.25 \log_{10}$ CCID₅₀/g) will be assigned the corresponding value of LLOQ or ULOQ.

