For each subject, the extent of viral shedding will be calculated as the area under the curve (using the linear trapezoidal method) of \log_{10} -transformed values of viral concentration in stool samples as determined using quantitative PCR (viral identity) and CCID₅₀ (titer) from samples taken through 28 days following each vaccine dose, and this continuous variable will be summarized. If a subject is missing two consecutive shedding data points among those intended to be tested for this computation due to samples not provided and/or unevaluable samples, the subject will have a missing value. This requirement regarding consecutive missing samples may be relaxed at the analysis stage if sample size for this computation is significantly impacted. Additionally, the Sheding Index Endpoint (SIE) will be computed as the arithmetic mean of \log_{10} CCID₅₀/g obtained from Days 7, 14, 21, and 28. Here, a single missing daily value will lead to a missing

SIE value, although windows of +/- 2 days will be applied to sample availability. If samples are available at both +1 (+2) and -1 (-2), then the mean \log_{10} CCID₅₀/g from these two days will be used for this computation. This will be summarized as a continuous variable using the same methods for daily viral shedding described above.

Additionally, a summary of time-to-shedding-cessation will be prepared using Kaplan-Meier methods. The day of cessation of shedding will be defined as the day of the first sample negative for shedding after which the following two samples are also negative. Summaries will be produced using Kaplan-Meier methods, and will include quartiles and corresponding 95% confidence intervals, as well as the estimated shedding rate at study days 3, 5, 7, 10, 14, 21, and 28 with corresponding 95% confidence intervals. Subjects who are positive for type 2 viral shedding at their last available assessment date with an evaluable stool sample, or who fail to cease shedding prior to a 2nd dose will be right-censored at the last time point they were known to be shedding virus. The time-to-shedding-cessation curves will be displayed graphically, and the comparison of the difference in time to shedding cessation curves between candidate groups in study M4 and corresponding controls subjects from study UAM1 will be conducted by computing the two-sided log-rank p-value.

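### On the UAM1 stool schedule the three-negative cessation rule records no event after Day 14 in Group 1, or in Group 2 after dose 2, while UAM4 can, so the log-rank comparison can lean toward the candidates

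*SAP*

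**What the plan says.** **Samples used.** SAP 6.7.1 plans all shedding analyses on samples "collected at Days 0-10, 14, 21, 28, and 42 following each dose (with day of vaccination defined as Day 0", plus any further samples needed to establish the end of shedding. It does not separate UAM1 from UAM4.

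**Event and censoring.** The same section dates cessation at the first negative sample that is followed by two more negatives. It names two kinds of censored subject: those positive at their last evaluable sample, and those who have not ceased before a second dose. Both are "right-censored at the last time point they were known to be shedding virus". Candidate and UAM1 curves are compared by a two-sided log-rank test, which Protocol 10.1.3 sets at 5%. After dose 1, the one-dose and two-dose groups are pooled (SAP 6.7).

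**UAM1 stool schedule (Protocol Appendix 3).** Group 1: "Daily collection on Days 0 to 10 plus collection on Days 14, 21 and V4 minus 1 or 2 days". Group 2: "After each vaccine dose, daily collection on Days 0 to 10 plus collection on Days 14, 21 and V4 minus 1 or 2 days". Day 42 in Group 1 is a remote contact only: "Daily remote contact (text message by sms, WhatsApp or email) from Day 0 to Day 10 and also on Day 21 and 42". The synopsis gives no extended sampling.

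**UAM4 stool schedule (Protocol 8.1).** After the daily samples, Groups 1 and 3 have "collection on Days 14, 21, V4 minus 1 or 2 days and V5 minus 1 or 2 days". For the two-dose groups the late samples are "V4 minus 1 or 2 days (= V7 minus 1 or 2 days after 2nd vaccination) and V8 minus 1 or 2 days", and V8 comes only after dose 2. Protocol 9.1 extends sampling until three consecutive negatives "if type 2 virus shedding is detected by PCR on one of the last 3 scheduled stool samples".

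**The concern.** The event rule needs three negatives in a row, so the latest day on which cessation can be recorded depends on where a study's sampling stops. UAM1 stops earlier than part of UAM4. The same shedding history can then be an event in UAM4 and not in UAM1, which makes Sabin 2 recipients appear to shed longer.

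The log-rank test is the planned comparison of shedding duration with Sabin 2. Protocol 6.1 (Table 1) lists reduced shedding as a possible effect of one of the modifications, so a spurious finding that the candidates stop sooner would look like support for it.

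**Working it through.** The documents give no power or event count for this test, so there is no stated figure to reproduce. The check has two parts: schedule arithmetic, then a null simulation.

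**1. Latest recordable event.** An event needs its own negative and two later ones, so the latest event day is the third-from-last sample. Nominal days are used: V4 minus 1 or 2 days is Day 26-27, or Day 24-29 with the visit window of 2 days either way.

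| Series | Last four samples | Latest event day |
|---|---|---|
| UAM1 Group 1; UAM1 Group 2 after dose 2 | 10, 14, 21, 27 | 14 |
| UAM4 Groups 1 and 3; Groups 2 and 4 after dose 2 | 14, 21, 27, 41 | 21, or later with extension |
| Two-dose groups after dose 1, both studies | 10, 14, 21, 27 | 14 |
| The same, if the Day 28 pre-dose stool counts | 14, 21, 27, 28 | 21 |

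Only the first two rows differ between studies. After dose 1 that contrast covers 50 of the 100 subjects in each pooled arm. After dose 2 it covers all 50.

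**2. The same history under each schedule (first two rows).**

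| Last positive | UAM1 | UAM4 |
|---|---|---|
| Day 10 | negative 14, 21, 27: event Day 14 | event Day 14 |
| Day 14 | negative 21, 27 only: no event, and no censoring rule stated | negative 21, 27, 41: event Day 21 |
| Day 21 | negative 27 only: no event, and no censoring rule stated | negative 27, 41 and extension: event Day 27 |
| Day 27 | positive at last sample: censored Day 27 | negative 41 and extension: event Day 41 |

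**3. Why this biases the test.** Unequal follow-up alone does not bias a log-rank test. Here, UAM1 subjects last positive on Day 21 or 27 are still in the risk set when UAM4 events occur on Day 21 or later, yet no event can be recorded for them. Censoring at last positive also depends on the outcome.

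**4. What drives the size.** The key quantity is the share still shedding after about Day 14. For exponential durations it is roughly (proportion shedding) × 0.5^(14/median):

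- 40% shedding, median 5 days: 0.40 × 0.5^2.8 = 0.40 × 0.144 = 0.06
- 80% shedding, median 14 days: 0.80 × 0.5 = 0.40

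The simulated UAM1 censored shares after dose 2 match: 6%, and 41-42%. UAM4 had 0% in both cases.

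**5. Null simulation.** Shedding is identical in both studies, durations are exponential, PCR detection is 95% per sample, and UAM4 extension sets come about 3 weeks apart. Subjects who never reach three negatives are censored at last positive. There were 700 replicates per pooled cell and 1,000 per post-dose-2 cell. The table gives the false rate of candidates stopping sooner (nominal 2.5%). The pooled range shows the Day 28 stool counted or not.

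| Assumed shedding | Post-dose-1, 100 v 100 | Post-dose-2, 50 v 50 |
|---|---|---|
| 40%, median 5 days | 3.4-4.0% | 3.5% |
| 40%, median 14 days | 5.1-8.1% | 8.9% |
| 80%, median 10 days | 8.3-10.4% | 13.0% |
| 80%, median 14 days | 11.4-14.1% | 18.3% |
| 80%, median 28 days | 11.7-13.3% | 20.7% |

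The opposite error, control stopping sooner, was 0-3%. The simulation standard error near 2.5% is √(0.025 × 0.975 / 1000) = 0.5 percentage points, so the first row is close to nominal.

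Censoring at the last sample instead gave 8-16% pooled and 10-27% post-dose-2 (80% shedding). A second simulation covered both censoring choices. It gave about 2-5% with 40% shedders and a 5-day median. With 90% shedders and a 20-day median it gave 25-29% pooled and 35-47% post-dose-2.

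**6. After the fix.** With UAM4 cut to the UAM1 schedule, the first simulation gave 1.7-3.5% and equal censoring in the two studies. The second gave about 1-4%.

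**The case against.** The strongest reply is that the SAP never says how to treat a UAM1 subject with only one or two trailing negatives, in Group 1 or in Group 2 after dose 2. If such subjects are counted as events at their first trailing negative, the bias nearly vanishes: 1.5-3.5% each way. The gap is real. But that reading contradicts the SAP's own event definition, which requires two further negatives. Keeping the definition leaves the bias in place, whether censoring is at last positive or at last sample.

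Four further points stand and limit the claim:

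- The endpoint is exploratory, SAP 6.7 calls the shedding analyses descriptive in nature, and no decision rule attaches to the p-value.
- AUC, the shedding index and daily positivity do not use the three-negative rule.
- UAM1 is available only as a synopsis, so later sampling in its full protocol cannot be excluded.
- The durations in Protocol 1.3.1, about 2 and 4 weeks, are for IPV-primed adults. SAP 6.7.2 reports only 2 qualifying post-dose-1 UAM1 samples. That concerns titre rather than duration, but it gives no support for assuming heavy shedding.

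Some stronger readings are tempting but fail on the documents:

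- That the whole candidate arm is followed to Day 42 after dose 1. Groups 2 and 4 are not.
- That Day 14 is the limit throughout UAM1. Group 2 after dose 1 could reach Day 21 if the Day 28 stool counts.
- That a two-dose subject last positive on Day 14 after dose 1 is treated differently by study. The rule on not ceasing before dose 2 works the same way in both.

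**Conclusion.** The comparison is wrong as written. On the UAM1 synopsis schedule, one event rule applied to two sampling schedules can record late cessation in UAM4 but not in UAM1. This affects half of the pooled post-dose-1 comparison and all of the post-dose-2 comparison. If subjects without three terminal negatives are not events, as the definition implies, the direction is toward the candidates stopping sooner.

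The size cannot be fixed from the documents. It is negligible if shedding is short and uncommon, and several times the nominal 2.5% if many subjects still shed after about Day 14. The percentages rest on assumed shedding rates and durations and show orders of size, not estimates for this trial. A reader might infer that the log-rank result will be materially misleading here; without OPV-primed durations the documents do not establish that. The primary immunogenicity and safety analyses are untouched.

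**What to change.** For every UAM4-UAM1 comparison of time to cessation, state in SAP 6.7.1 that:

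1. Both studies use only the common samples after each dose: Days 0-10, 14, 21 and the sample just before Day 28.
2. One event definition applies to both studies. The three-negative rule may stay.
3. The Day 28 pre-dose stool is assigned the same way in both studies.
4. One stated censoring rule covers subjects with fewer than three terminal negatives.
5. UAM4 Day 42 and extension samples are reported descriptively, for UAM4 only.

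Correct the sentence that lists Day 42 after each dose, since neither UAM1 nor the UAM4 two-dose groups after dose 1 have that sample. Confirm from the UAM1 sample dates that collection did end at about Day 27. Also reconcile Protocol 10.1.3, which measures time to the last positive day, with the SAP, which uses the first negative day; SAP Section 7 does not list this difference.

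The cost is SAP wording and one data filter. SAP 6.7.1 already stops at Day 28 for AUC, the shedding index and the tabulated Kaplan-Meier estimates. The downside is small: the comparison says nothing about differences beyond the common window, and if the three-negative rule is kept without the Day 28 stool, the last recordable event is Day 14 in both studies.

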Non-inferiority comparisons will be conducted by computing the difference in endpoint between each candidate vaccine and the UAM1 Sabin 2 control (novel minus comparator), with corresponding two-sided $\alpha = 0.05$ confidence intervals, with inference drawn from comparison of the lower confidence limit to the non-inferiority margin.

Score-based confidence intervals will be used for binary comparisons, asymptotic normal-based methods will be used for GMTs, and bootstrap methods will be used for median titers and other continuous endpoints.

Immunogenicity comparisons will be based on the combined data from each site in this study compared to the single-site data from the historical control study, UAM1. In the event that between-site comparisons within this study indicate that significant differences in outcomes (two-sided tests for differences at $\alpha = 0.05$) exist between sites, additional

comparisons for all immunogenicity endpoints will be added to compare vaccine candidates using only data at the site in common between both studies. Comparisons of binary endpoints between sites in this study will be based on 95% two-sided score intervals for the difference; comparison of continuous endpoints will be based in two-sided 95% bootstrap-based confidence intervals for the difference in medians (median titer), or normal-based methods (for GMTs). Differences between sites will be indicated by a nominal value (percent/median/mean difference of zero) excluded from the confidence interval coverage region.

Viral Shedding

For each group (excluding Group 7), site, and time point, viral shedding positivity and concentration will be summarized. For each subject, a viral shedding index will be calculated as the average of \log_{10} -transformed values of viral concentration in stool samples as determined using quantitative PCR (viral identity) and CCID₅₀ (titer) from select stool samples taken following each vaccine dose, and this index will be summarized by group. The time to cessation of shedding, defined as the time interval between administration of vaccine and the last day of shedding positivity prior to cessation, will be assessed with Kaplan-Meier methods to describe and compare the duration of shedding.

Descriptive analysis and plots of the reverse cumulative distribution of the viral shedding index will be generated.

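### The 28-day shedding AUC is not set to missing when only the last stool is absent, so a Day 21 area counts as complete and understates extent in subjects still shedding at Day 21 or Day 28

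*SAP*

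**What the plan says.** SAP 6.7.1 states that "the extent of viral shedding will be calculated as the area under the curve (using the linear trapezoidal method") on log10 viral concentration, with the window given as "samples taken through 28 days following each vaccine dose". The AUC is missing under one condition only: "If a subject is missing two consecutive shedding data points among those intended to be tested for this computation", whether because the samples were not provided or could not be evaluated. The next sentence adds: "This requirement regarding consecutive missing samples may be relaxed at the analysis stage", if the number of usable subjects suffers, and sets no limit on this.

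The samples are those "collected at Days 0-10, 14, 21, 28, and 42 following each dose". In the Protocol's Time and Events Schedule (8.1, footnote l) the stool that the SAP calls Day 28 is tied to the visit: "daily collection on Days 0 to 10 plus collection on Days 14, 21, V4 minus 1 or 2 days".

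Three other provisions bear on the point:

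- SAP 5.3 assumes data are missing completely at random and plans no imputation.
- SAP 6.7.1 also defines the SIE, the mean of Days 7, 14, 21 and 28. One missing day makes it missing, after a ±2-day allowance.
- The AUC is compared with UAM1 in OPV-vaccinated subjects as a difference in medians with a bootstrap 95% interval. In the IPV groups it is only summarised.

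**The concern.** The rule on two consecutive samples suits gaps inside the curve, where a straight line between the neighbouring points stands in for the lost value. At the end of the curve there is no later point to draw to. The area stops at the last sample present, and the SAP neither requires a Day 28 value nor says how to close the curve. The SAP does not say in words that a 21-day area counts as a 28-day one; this follows from the rule, the ban on imputation and the silence about the end point.

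Collection is sparse after Day 10, so a single stool governs the last quarter of the window. The error is never upward, and it falls only on subjects positive at Day 21 or Day 28, whose extent of shedding the measure most needs to capture. The same subject would have a missing SIE and an apparently complete AUC.

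**Working it through.** The plan gives no figure for the AUC, so there is none to reproduce. The check applies the SAP's rule to its own schedule.

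**Inputs from SAP 6.7.1.** Nominal days 0–10, 14, 21 and 28. PCR-negative samples count as 0. Positive samples below or above the quantifiable range count as 2.75 or 8.25 log10 CCID50/g.

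**Assumptions.** The titre profiles below, with Day 0 set to 0. The documents give no daily titres and no rate of missing last stools.

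**Formula.** AUC = Σ (t[k+1] − t[k]) × (y[k] + y[k+1]) / 2. If only Day 28 is missing, the last term drops out:

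lost area = 7 × (y21 + y28) / 2 = 3.5 × (y21 + y28).

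**Examples.**

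- Flat at c from Day 1: full area 0.5c + 27c = 27.5c; lost 7c; 7/27.5 = 25.5% at any level.
- Decline from 6 at Day 1 to 2.75 at Day 28: y21 = 6 − 3.25 × 20/27 = 3.593. Full area 3 + 27 × (6 + 2.75)/2 = 121.1; lost 3.5 × (3.593 + 2.75) = 22.2.
- Same decline, but negative at Day 28: lost 3.5 × 3.593 = 12.6.

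| Assumed profile | Full AUC | Day 28 missing | Change |
|---|---|---|---|
| Flat at 2.75 | 75.6 | 56.4 | −25.5% |
| Flat at 8.25 | 226.9 | 169.1 | −25.5% |
| 6 falling to 2.75 at Day 28 | 121.1 | 98.9 | −18.3% |
| Same fall, negative at Day 28 | 111.5 | 98.9 | −11.3% |
| 6 falling to 2.75 at Day 14, then negative | 69.5 | 69.5 | 0% |
| 6 falling to 2.75 at Day 10, then negative | 47.9 | 47.9 | 0% |

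If the last stool falls on Day 27 rather than Day 28, the flat profile loses 6c of 26.5c, or 22.6%.

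**Interior gaps, for contrast.** Losing Day 14 or Day 21 leaves a flat profile unchanged. In the fifth row, losing Day 21 gives 79.1 instead of 69.5; in the fourth, 101.9 instead of 111.5. Interior errors can go either way; the end error cannot go up.

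**If the rule is relaxed.** Were Days 21 and 28 both allowed to be missing, a flat profile would lose 14c of 27.5c, or 50.9%.

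**The case against.** The strongest reply is that this hardly matters for the planned comparison. Shedding analyses are exploratory. A difference in medians does not move if a late shedder drops but stays above the median. UAM1 controls seem to have shed little at high titre: SAP 6.7.2 counts only 2 post-dose-1 samples from UAM1 that qualify for the neurovirulence assay, where the cutoff is 4.0 log10 CCID50/g. Poor late return would show in the SAP 6.4 table of evaluable stools by collection day, and SIE, daily positivity and time to cessation are reported alongside.

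Much of this stands. It limits the effect on the comparison but does not make the individual AUC values right. The ranking argument is incomplete: the flat 2.75 profile belongs above the fifth-row subject (75.6 against 69.5) but falls below once truncated (56.4). Few samples above 4.0 log10 also does not exclude low-level late shedding.

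The schedule offers a partial remedy in two-dose groups. UAM4 marks a stool at Day 28 before the second dose, and UAM1 Group 2 also collects on Day 0 of its second dose. Either could close the post-dose-1 curve. The SAP does not say that it will, and there is no such stool in one-dose groups or after the second dose.

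A reader might go further and infer that missing last stools would appear as a difference between vaccine and control. The documents do not support that. They give no rate of missing last stools in either study and nothing to show that the rates differ; the differing reminder schedules (Protocol 8.1 and Appendix 3) are not evidence of return.

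**Conclusion.** The gap is real and minor. As written, SAP 6.7.1 accepts an area ending at Day 21 as a 28-day value. For a subject positive at Day 21 or Day 28 this understates the AUC, by 11% to 26% under the profiles assumed above; for a subject negative at both it changes nothing. That range describes those profiles and is not a bound.

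The effect on the median comparison with UAM1 cannot be determined from the documents and may be small in OPV-vaccinated subjects. The IPV-group summaries may be more exposed: Protocol 1.3.1 reports median shedding of about 2 and 4 weeks for the two candidates in IPV-primed adults, so late positivity is expected there. The primary endpoint, the SIE and time to cessation do not use this rule.

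Nor should the point be read as the SAP having replaced an average with a total. The Protocol (10.1.3, Viral Shedding) says "a viral shedding index will be calculated as the average of" log10 values, and the SAP keeps an average in the SIE, which handles a missing Day 28 properly.

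**What to change.** Add to SAP 6.7.1 that the AUC after a given dose is missing if the final scheduled sample of its 28-day window is missing or unevaluable, after the same ±2-day allowance as for the SIE, and that relaxing the rule on consecutive samples cannot waive this. State that the Day 28 stool collected before the second dose may serve as the closing sample in the two-dose groups of both studies. Appendix 3 does not mark the UAM1 stool as pre-vaccination, so confirm that it was.

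Say also what the ±2 days are counted from. Visit 4 may fall on Days 26 to 30 and the stool is due 1 or 2 days earlier, so an on-schedule sample can fall on Days 24 to 29. Counting from Day 28 would reject Days 24 and 25. Use one definition for AUC and SIE.

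Two alternatives should be avoided:

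- **Dividing by observed time.** For the fifth-row subject this gives 69.5/21 = 3.31 instead of 69.5/28 = 2.48, 33% too high. It moves the error onto subjects who stopped early.
- **Interpolating to the Day 42 stool.** UAM1 stool collection ends before Visit 4 (Visit 7 after a second dose), so the two studies would be handled differently.

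The cost is a short SAP addition, one programming check and a few missing AUC values. Dropping those subjects relies on the missing-completely-at-random assumption that SAP 5.3 already makes.
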